### 8.6 Visual Analog Scale Standardization

The Visual Analog Scale (VAS) forms used in this study may have varied in length, ie, the Case Report Form (CRF) scale length may have varied by subject or visit. To ensure consistency across subjects and visits, all VAS scores are standardized to account for these differences. The VAS standardized score will be derived by converting the measure length to a maximum score of  $VAS_{max}$  with one decimal place as follows:

$$\text{Score} = \text{Measured Result (mm)} * VAS_{max} / \text{CRF Scale Length (mm)}$$

The maximum score for each VAS is discussed in the analysis section.

## 9. Disposition of Subjects

The number of subjects screened, along with the number and percentage of screen failure subjects, will be summarized for all screened subjects.

The number and percentage of subjects included in each analysis population will be summarized by treatment group and overall for all randomized subjects.

A listing of subjects excluded from the PP population and the reason(s) for exclusion will be provided. Reasons will include screen failure, major protocol violation, and  $>10\%$  missing data on the Glia Questionnaire.

The number and percentage of subjects who enter, complete, and discontinue the Study Treatment Phase, and the Cross-over Phase will be summarized by treatment group and overall for the ITT population. A listing of discontinued subjects including the date and phase discontinued and the reason for discontinuation will be provided.

A subject listing will be provided for all protocol deviations. The listing will include the date of the deviation, the deviation category, the deviation description, and the classification of whether the deviation was judged to be major or minor in a blinded review.

In addition, subject listings will be provided that include informed consent date, randomized treatment and actual treatment.

## **10. Demographic Variables and Iris Color**

The demographic variables collected in this study include age, sex, race, ethnicity, and iris color. Subjects who record more than one race will be grouped into a single category denoted as multi-racial. Demographic variables will be summarized for the ITT population.

Age will be reported in years and calculated using the following formula:

$$\text{Age} = (\text{Informed Consent Date} - \text{Date of Birth}) / 365.25, \text{ truncated as an integer}$$

Age will be summarized, overall and by treatment, using continuous descriptive statistics. Age will also be categorized as follows: < 65 years and  $\geq$  65 years. Age will be reported in years.

The number and percentage of subjects will be presented, overall and by treatment, for age category, sex, race, ethnicity, and iris color.

A subject listing that includes all demographic variables will be provided.

## **11. Medical History and Concomitant Medications or Devices**

### **11.1 Medical History**

Ocular and Non-Ocular medical history will be coded using version 22.0.

Ocular and Non-ocular medical history will be summarized using discrete summary statistics and presented by treatment group at the subject level by System Organ Class (SOC) and Preferred Term (PT) using the Safety population. If a subject reports the same PT multiple times within the same SOC, then that PT will only be reported once within that SOC. As with the PT, if a subject reports multiple conditions within the same SOC, that SOC will only be reported once.

Listings of medical history will be generated separately for ocular and non-ocular data.

### **11.2 Prior and Concomitant Medications or Devices**

Concomitant medications will be coded using WHO ATC/DDD Index 2019, searchable version of the complete Anatomical Therapeutic Chemical (ATC) index with defined daily doses (DDDs) and summarized

to the therapeutic drug class (Anatomical Therapeutic Chemical [ATC] 4 classification) and preferred name. If the ATC 4 classification is not provided, then the next lowest classification that is provided in the coding dictionary will be used. The preferred name will be defined as the active ingredient; if the active ingredient is not provided or includes more than two ingredients (eg, multivitamins), then the drug name will be summarized as the preferred name. Any uncoded terms will be summarized under the ATC classification and preferred name of "Uncoded."

Concomitant medications are defined as those medications listed as having been taken 1) prior to initiation of study drug administration and continuing for any period of time following the first administration of study drug or 2) at any time following the first administration of study drug.

Concomitant medications will be summarized using the Safety population. Medications will be tabulated for each treatment group using frequencies and percentages. Subjects may have more than one medication per ATC text. At each level of subject summarization, a subject will be counted once if he/she reports one or more medications. Percentages will be based on the number of subjects in each treatment group. Listings of concomitant medications will be generated.

Prior medications are defined as those medications or devices with start and end dates before the first dose of study drug. Prior medications or devices will be listed only.

## **12. Treatment Exposure and Compliance**

The duration of treatment exposure by study phase will be calculated in days.

Duration of treatment exposure during the Study Treatment Phase:

Duration (days) = Date of last dose in Study Treatment Phase minus date of first dose in Study Treatment Phase + 1.

Note that the last dose in the Study Treatment Phase is expected to be the morning of Visit 5.

Duration of treatment exposure during the Placebo Crossover Phase:

Duration (days) = last dose date in Placebo Crossover Phase - first dose date in Placebo Cross-over Phase + 1.

Compliance during the Study Treatment Phase:

Compliance = (total count of time entries for drug application in Study Treatment Phase) x 100 / (treatment duration in for the Study Treatment Phase x 2 applications per day)

Compliance during the Placebo Crossover Phase:

Compliance = (total count of time entries for drug application in Placebo Crossover Phase) x 100 / (treatment duration in for the Placebo Crossover Phase x 2 applications per day)

Note that the first dose in the Placebo Crossover Phase is expected to be the day following Visit 5.

Duration of treatment exposure for each subject exposed to study drug will be summarized with continuous descriptive statistics for each treatment group and study phase using the Safety population. A subject listing of treatment exposure will also be produced.

### **13. Efficacy Analyses**

The efficacy measures in this study are described below. All analyses will be conducted separately for the Study Treatment Phase and the Placebo Cross-over Phase. Where applicable a worse eye at baseline will be determined for each individual sign or symptom. Analyses will include the worse eye and fellow eye separately.

#### **13.1 GLIA Ocular Surface Disease Symptoms Questionnaire, Clinic & Daily Diary**

The GLIA Ocular Surface Disease Symptoms Questionnaire will be collected in the clinic at every visit (both pre-dose and post-dose at Visit 2) and will be collected via subject daily diary.

A VAS ranging from None to Most Severe will be used to assess subject's symptom severity, by eye, for the following:

- Ocular discomfort
- Dryness
- Grittiness
- Burning
- Stinging
- Foreign body sensation
- Ocular pain
- Conjunctival redness
- Itching
- Mucus discharge
- Photophobia
- Blurred or cloudy vision
- Air flow sensitivity
- Lid redness
- Lid sticking

Subjects will be asked to rate each symptom by placing a vertical mark on the horizontal line to indicate the level of severity. The result (in mm) will be measured from the left endpoint (None) to the slash marked by subject on the line.

For each symptom, a score is derived by converting the measure length to a maximum score of 10 with one decimal place as follows:

### 13.1.1 ANALYSIS OF GLIA OCULAR SURFACE DISEASE SYMPTOMS QUESTIONNAIRE COLLECTED IN CLINIC

#### The primary analysis (Study Treatment Phase):

For each symptom, an analysis of covariance (ANCOVA) will be used to compare change from baseline between Pro-ocular and placebo with adjustments for baseline symptom score (BASELINE), treatment group (TRT), visit (VISIT), and treatment x visit interaction (TRT\*VISIT) as the explanatory variable. The least squares (LS) means, LS mean differences, SEs, two-sided 95% CIs for the difference in LS means, and two-sided p-values (unadjusted and Benjamini-Hochberg adjusted p-values) will be reported for the treatment effect at each visit and all visits combined. Model effects will also be displayed.

SAS pseudo-code for this model follows:

```
PROC MIXED data=indata order=internal;
  By EYETYPE;
  class TRT VISIT;
  model CFB = TRT BASELINE VISIT TRT*VISIT;
  LSMEANS TRT VISIT TRT*VISIT / CL PDIFF;
run;
```

The ITT population will be used as the primary population using LOCF for imputation.

Sensitivity analyses will include the ITT population and PP population using observed cases.

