## 2. Study Objectives

The primary objective of this study is to evaluate the safety and efficacy of Pro-ocular™ 1% topical gel administered twice daily for 70 days in ameliorating symptoms and signs of chronic ocular graft-versus-host disease (GvHD).

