### 3. Study Design and Procedures

#### 3.1 General Study Design

This is a Phase 2 randomized, single-center, parallel, double-masked, placebo-controlled study assessing the safety and efficacy and the of Pro-ocular™ 1% topical gel administered twice daily for 70 days in ameliorating symptoms and signs of chronic ocular GvHD.

Thirty-three subjects will be enrolled and randomly assigned in a 2:1 ratio to one of two treatments arms:

- Pro-ocular™ 1% topical gel (22 subjects)
- Placebo (11 subjects)

After a Screening visit to assess eligibility, subjects will enter a double-masked 70-day Study Treatment Phase (Visit 2 – Visit 5). Upon completion of the double-masked phase, subjects who were originally randomized to Placebo will cross-over into an open-label Placebo Cross-over Phase and will receive Pro-ocular 1% topical gel for twice-daily administration over 6 weeks (Visit 5 – Visit 7).

Analyses will be conducted separately for the Study Treatment Phase and the Placebo Cross-over Phase. The analysis of the Study Treatment Phase is the Primary analysis, and the analysis of the Placebo Cross-over Phase is secondary.

Study visits will be referred to in all tables and listings as the expected study day corresponding to the visit to enable reviewers to understand the assessment timing without referring to the protocol visit schedule. Listings, tables and figures will include visits and study days in the following format: Visit 1 (Day -14), Visit 2 (Day 1), Pre-Dose, Visit 2 (Day 1), Post-Dose, Visit 3 (Day 14), Visit 4 (Day 42), Visit 5 (Day 70), Visit 6 (Week 3) and Visit 7 (Week 6).

**Table 1** shows the scheduled study visits, their planned study day, and the acceptable visit window for each study visit.

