**Table 2. Schedule of Visits and Assessments**

Blue = Conducted at DFCI		Study Treatment Phase				Placebo Cross-over Phase	
Black = Conducted at MEEI	Visit 1 (Screening)	Visit 2 Baseline & First Drug Application	Visit 3	Visit 4	Visit 5	Visit 6	Visit 7
	Day -14 to -1	Day 1	Day 1	Day 14±2	Day 42±3	Day 70±3	3 weeks
Procedure		Pre-Dose	30-60 min Post-Dose				
2-digit screening number	X						
Informed consent	X						
Visual acuity (current correction)	X					X	
NIH Eye Score	X					X	X
Facial photo		X				X	X
Slit Lamp Biomicroscopy	X			X	X	X	X
Undilated Fundoscopy Exam	X					X	
Corneal and Conjunctival Staining	X			X	X	X	X
Intraocular Pressure	X					X	X
Inclusion/Exclusion Criteria	X						
Medical/Ophthalmology history and updates	X	X		X	X	X	X
Prior and concomitant medication query	X	X		X	X	X	X
Concomitant medications (BMT)	X				X	X	X
Medical History & Physical (BMT)	X						
Demographic data	X						
Video of face & eyes (1 minute)		X	X	X	X	X	X
TearScan Examination		X	X	X	X	X	X
Urine pregnancy test	X					X	
Modified SANDE Questionnaire	X			X	X	X	X
GLIA Ocular Surface Disease Symptoms Questionnaire	X	X	X	X	X	X	X
Adverse Event Query			X	X	X	X	X

Blue = Conducted at DFCI		Study Treatment Phase					Placebo Cross-over Phase	
Black = Conducted at MEEI	Visit 1 (Screening)	Visit 2 Baseline & First Drug Application		Visit 3	Visit 4	Visit 5	Visit 6	Visit 7
	Day -14 to -1	Day 1	Day 1	Day 14±2	Day 42±3	Day 70±3	3 weeks	6 weeks
Screen Pass/Fail	X							
3-digit random number	X							
BMT systemic evaluation & GvHD assessment	X				X	X		X
Standard GvHD, CBC, and metabolic labs	X				X	X		X
Endocrine panel	X				X	X		X
Daily diary collected				X	X	X	X	X
Study drug collected/ accountability				X	X	X	X	X
Study drug application (in-clinic)		X						
Study Drug Dispensed		X		X	X	X	X	
Daily Diary Dispensed			X	X	X	X	X	

Abbreviations: CBC = Complete Blood Count, DFCI = Dana-Farber Cancer Institute, GvHD = graft-versus-host disease, MEEI = Massachusetts Eye and Ear Infirmary.

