### 8.5 Adjustments for Multiplicity

The Benjamini-Hochberg procedure will be used to adjust for multiplicity for the primary analysis of the key efficacy variables.

The Benjamini-Hochberg procedure is as follows:

- 1) Sort the original p-values from smallest to largest
- 2) Assign ranks to the original p-values smallest to largest
- 3) Calculate the p-values' adjusted Benjamini-Hochberg critical value as follows:

Adjusted critical p-value = (rank of original p-value/ number of tests i.e. largest rank)\*false discovery rate, or  $\alpha = 0.05$ .

- 4) Compare the original p-values to adjusted critical p-values; find the largest original p-value that is  $\leq 0.05$ ;
- 5) Reject the null for any original p-values that is the largest original p-value in 4) or smaller than the p-value in 4).

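### SAP 13.1.1 and 13.2.1 test every visit and a combined effect but name no primary contrast or Benjamini-Hochberg family; the combined GLIA effect appears to give the first-dose reading the same weight as Day 70

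*SAP*

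**What the plan says.** SAP 13.1.1 fits change from baseline for each GLIA symptom on treatment, baseline score, visit and treatment-by-visit, separately by eye type. Estimates, confidence intervals and p-values, both unadjusted and adjusted, "will be reported for the treatment effect at each visit and all visits combined". The code line that produces them is "LSMEANS TRT VISIT TRT*VISIT / CL PDIFF". SAP 13.2.1 applies the same analyses to SANDE.

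On timing, SAP 13.1 says GLIA is "collected in the clinic at every visit (both pre-dose and post-dose at Visit 2". SAP 3.1 gives the post-dose reading its own label in the list of visits: "Visit 2 (Day 1), Post-Dose, Visit 3 (Day 14), Visit 4 (Day 42), Visit 5 (Day 70". The schedule in SAP Table 2 places it at "30-60 min Post-Dose". The clinic record form in the protocol appendix allows 30 to 90 minutes, and the two should be reconciled. SANDE is collected at Visit 1 and from Visit 3 onwards (SAP 13.2).

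On multiplicity, SAP 8.5 says: "The Benjamini-Hochberg procedure will be used to adjust for multiplicity for the primary analysis of the key efficacy variables". It describes the divisor as the number of tests but gives no figure. The key variables (SAP 2.2) and hypotheses (SAP 2.5) name no visit. Where the SAP calls an analysis primary in sections 1 and 3.1, it means the Study Treatment Phase as a whole.

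**The concern.** Two things are left unsettled. First, each symptom has several candidate results, one per visit plus the combined one, and nothing says which one decides. Without a fixed family the adjusted p-values promised in 13.1.1 cannot be computed uniquely, and a contrast could be chosen after results are seen. The investigator unmasks each subject after Visit 5 (SAP 4.2), before the primary lock that closes the phase (SAP 6), so a choice fixed in writing is worth more here than usual.

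Second, the combined GLIA effect appears to mix a reading taken within about an hour of the first application with readings after 2, 6 and 10 weeks of dosing, all equally weighted. That can understate an effect that builds over weeks, or give credit to one that is present only at first application. The combined SANDE effect contains no such reading, so the same label covers two different quantities.

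**Working it through.** The plan gives no visit weights and no number of tests, so there is no figure of its own to reproduce.

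**1. Levels of VISIT for GLIA.** SAP 8.3 defines baseline as the last value before the first dose, which for GLIA is Visit 2 pre-dose. The post-dose reading is therefore post-baseline, and SAP 3.1 labels it separately. The only stated limit on visits in the model is an upper cut at Visit 5 (SAP 13.1.1, additional analyses). This gives four levels: Visit 2 post-dose, Visit 3, Visit 4 and Visit 5. For SANDE there are three: Visits 3, 4 and 5.

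**2. Weights.** With treatment-by-visit in the model and no weighting option, the treatment LS-mean difference is the simple average of the visit-specific differences:

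combined = (d1 + ... + dK) / K

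For GLIA K = 4, so each level has weight 1/4 = 0.25. For SANDE K = 3, so each has 1/3. As a check, the model was fitted to 33 subjects (22 and 11) at four levels, with a unit effect placed at one level at a time. The combined difference was 0.25 each time, with complete and with unbalanced data.

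**3. Consequence for GLIA.** The profiles below are assumptions, in the order post-dose, Day 14, Day 42, Day 70.

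| Assumed effect | Combined, four levels | Post-dose removed | Day 70 |
|---|---|---|---|
| 1, 1, 1, 1 | 4/4 = 1.00 | 3/3 = 1.00 | 1 |
| 0, 1, 1, 1 | 3/4 = 0.75 | 3/3 = 1.00 | 1 |
| 0, 0.5, 0.8, 1 | 2.3/4 = 0.58 | 2.3/3 = 0.77 | 1 |
| 1, 0, 0, 0 | 1/4 = 0.25 | 0/3 = 0 | 0 |

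More generally, if the post-dose effect is a fraction a of a constant later effect, the combined effect is (a + 3)/4. It runs from 0.75 at a = 0 to 1.00 at a = 1.

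**4. Size of the family.** There are 15 GLIA symptoms, and SANDE yields frequency, severity and total.

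- One contrast, worse eye: 15 + 1 = 16 with the SANDE total only; 15 + 3 = 18 with all three scores.
- All visits plus combined, worse eye: 15 × (4 + 1) = 75 for GLIA, and 3 × (3 + 1) = 12 for SANDE; 75 + 12 = 87.
- Both eye types: 2 × 87 = 174.

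The threshold at rank r is 0.05 × r/m. At rank 1 this is 0.05/16 = 0.0031, 0.05/18 = 0.0028, 0.05/87 = 0.00057 and 0.05/174 = 0.00029. These apply only to the smallest p-value. At higher ranks the gap can close: rank 5 of 16 gives 0.0156, and rank 27 of 87 gives 0.0155.

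**The case against.** A reader might infer that the tested effect fails to match the study objective. The documents do not support that. The Visit 5 contrast is among those reported with an adjusted p-value, and the objective, "administered twice daily for 70 days in ameliorating symptoms and signs", gives 70 days as the duration of dosing, not Day 70 as the time of assessment. An average over the phase could also answer it.

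The 25% weight is an inference. The SAP never lists the levels of VISIT, and the post-dose reading could be regarded as a time point within Visit 2. The separate label in SAP 3.1 and the absence of any exclusion favour the four-level reading, but do not state it. It concerns GLIA only.

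A zero effect at first application is also questionable. Protocol I.c, on earlier uncontrolled use in this disease, reports relief starting at first application in most patients and growing with further use. That supports a rising effect, but not one that starts from nothing, so 0.58 and 0.75 illustrate what could happen and are not forecasts.

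A larger family does not tighten every threshold in proportion, because the critical values rise with rank. A 174-test family is unlikely, since the hypotheses in SAP 2.5 name the worse eye. Step 4 in SAP 8.5, read literally, looks for the largest p-value at or below 0.05, which would make the family size irrelevant to rejection. But step 3 computes rank-based critical values and step 4 begins by comparing against them, so this looks like loose wording.

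Protocol VI treats the tests as additional descriptors of the data. The SAP, however, states that its methods supersede the protocol's, and it sets hypotheses and a multiplicity rule.

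What remains after all this is the missing designation, the unlisted visit levels and the unstated family.

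**Conclusion.** The point holds in this form: several effects are tested for each key variable, none is designated, and the family to be adjusted is not fixed. Worse-eye counts from 16 to 87 are defensible, and the threshold for the smallest p-value moves from 0.0031 to 0.00057 between them. The effect on larger p-values depends on the whole set of results.

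On the plain reading, the combined GLIA effect gives a reading taken within about an hour of the first application the weight of Day 70, while the combined SANDE effect contains none. The loss relative to Day 70 is nil for an immediate, constant effect and one quarter if the effect is absent at the first reading and complete afterwards. A purely immediate effect would still show at a quarter of its size. These sizes rest on assumed profiles and on Visit 2 post-dose being a level of VISIT.

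**What to change.** In SAP 13.1.1 and 13.2.1, before unmasking:

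- List the levels of VISIT as Visits 3, 4 and 5 for both questionnaires. Report the GLIA Visit 2 post-dose reading separately, as onset of effect.
- Designate one worse-eye treatment contrast as primary. Visit 5 is the clearest; an equally weighted average of Visits 3 to 5 is acceptable if written down.
- In SAP 8.5, define the family as that contrast for the 15 GLIA symptoms plus the named SANDE score or scores, and give its size: 16 with the total only, 18 with total, frequency and severity. Reword step 4 so that the comparison is with the rank-based critical value.
- Report the other visits, the fellow eye and any non-primary contrast unadjusted, as supportive.

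The cost is SAP text and a small change to the code; no new data are needed. If Visit 5 alone is chosen and the effect is in fact constant over time, some precision is lost compared with an average.

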## **8.4 Data Analysis Conventions**

The Primary analysis will be performed by Statistics & Data Corporation (SDC) after the Study Treatment Phase is completed and the database has been locked and released for unmasking. An additional analysis will be completed once the Cross-over Phase is completed and the database for that portion is locked. Statistical programming and analyses will be performed using SAS® version 9.4 or higher. Output will be provided in rich text format (RTF) for tables, Excel format for tables and listings, and portable document format (PDF) for figures using landscape orientation for any PDF or RTF. All study data will be listed by subject, treatment, and visit (as applicable) based on all randomized subjects unless otherwise specified.

Summaries for continuous and ordinal variables will include the number of observations (n), arithmetic mean, standard deviation (SD), median, minimum, and maximum. Minima and maxima will be reported with the same precision as the raw values; means and medians will be presented to one additional decimal place than reported in the raw values. Standard deviations will be presented to two additional decimal places than reported in the raw values. Summaries for discrete variables will include counts and percentages. All percentages will be rounded to one decimal place (ie, XX.X%). Differences between active treatment group and placebo will be calculated as active minus placebo and change from baseline will be calculated as follow-up visit minus baseline.

All statistical tests will be two-sided with a significance level of 0.05 ( $\alpha = 0.05$ ) unless otherwise specified. Confidence intervals (CI) for differences between treatment groups will be two-sided at 95% confidence intervals. All p-values will be rounded to 4 decimal places; p-values less than 0.0001 will be presented as "<0.0001"; p-values greater than 0.9999 will be presented as ">0.9999."

Unless otherwise specified, summaries will be presented by treatment group and, where appropriate, visit. Listings will be sorted by treatment group, subject number, visit/time point, and parameter as applicable.

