### **13.1.2 Analysis of GLIA Ocular Surface Disease Symptoms Questionnaire Collected in Daily Diary**

The individual symptoms collected in the diary will be analyzed including all data across the 70-day treatment period, testing for a treatment effect using a generalized linear model that accounts for repeated measures, with an unstructured correlation structure, including terms for diary day. The LS means, LS mean differences, SEs, two-sided 95% CIs for the difference in LS means, and two-sided p-values will be reported. Model effects will be presented.

SAS pseudo-code for this model follows:

```
PROC MIXED data=indata order=internal;
  class TRT;
  model SYMPTOM = TRT DAY;
  repeated / subject=SUBJ type=UN ;
  random DAY;
  LSMEANS TRT / CL PDIFF;
run;
```

The LS mean (and SE) daily scores will be displayed graphically by treatment group across the 70 days. The mixed effects model analyses will be truncated at Visit 5 and any data presented after Visit 5 will be summarized with continuous descripted statistics.

Individual subject plots will also be presented displaying the subject score by day.

Analyses will be performed on the ITT population using observed cases only.

All Symptom scores collected via diary will be presented in a subject listing.

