### **13.2 Modified SANDE – Symptom Assessment iN Dry Eye Questionnaire**

The Modified SANDE – Symptom Assessment iN Dry Eye Questionnaire will be collected at Visit 1 and Visits 3 – 7.

A VAS will be used to assess subject's symptoms, by eye, for the following:

- Frequency of Symptoms
- Severity of Symptoms

First, the subject will be asked to place a vertical line to indicate how often, on average, their eyes feel dry and/or irritated. For frequency, the VAS ranges from Rarely to All the Time.

Second, the subject will be asked to place a vertical line to indicate how severe, on average, they feel their symptoms of dryness and/or irritation are. For severity, the VAS ranges from Very Mild to Very Severe.

The result (in mm) will be measured from the left endpoint to the slash marked by subject on the line.

For each symptom, a score is derived by converting the measure length to a maximum score of 100 with one decimal place as follows:

$$\text{Score} = \text{Measured Result (mm)} * 100 / \text{CRF Scale Length (mm)}$$

The total SANDE score is calculated by multiplying the frequency of symptoms score with the severity of symptoms score and obtaining the square root.

Subjects whose values are all 0 for a given symptom for all visits will not be included in the analysis for that symptom

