### 13.2.1 Analysis of SANDE Questionnaire

The primary and additional analyses for the modify SANDE Questionnaire will be the same as the Glia Ocular Surface Disease Symptoms Questionnaire. Both ANCOVA analyses will be truncated at Visit 5 and any data presented after Visit 5 will be summarized with continuous descripted statistics.

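### The primary clinic model for GLIA and SANDE declares no within-subject covariance, so its all-visits treatment test is too liberal if a subject's visits are positively correlated

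*SAP*

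**What the plan says.** SAP Section 13.1.1 specifies the primary clinic analysis of the GLIA questionnaire as PROC MIXED, run by eye type. Treatment and visit are the only CLASS variables, and the model statement is "model CFB = TRT BASELINE VISIT TRT*VISIT". There is no subject variable and no REPEATED or RANDOM statement. The accompanying prose lists the same four terms and names no covariance structure. Sections 8.1 to 8.6 and Section 16 add none.

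From this model, "two-sided p-values (unadjusted and Benjamini-Hochberg adjusted p-values) will be reported for the treatment effect at each visit and all visits combined". For the second key variable, Section 13.2.1 says: "The primary and additional analyses for the modify SANDE Questionnaire will be the same as the Glia Ocular Surface Disease Symptoms Questionnaire". Both ANCOVAs stop at Visit 5. Section 8.4 sets the level: "All statistical tests will be two-sided with a significance level of 0.05". Section 8.5 adds: "The Benjamini-Hochberg procedure will be used to adjust for multiplicity for the primary analysis of the key efficacy variables".

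The diary analysis in Section 13.1.2 is treated differently. It tests treatment "using a generalized linear model that accounts for repeated measures, with an unstructured correlation structure, including terms for diary day", and its code names the subject in a REPEATED statement.

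**The concern.** Without a REPEATED or RANDOM statement, PROC MIXED fits independent, equal-variance errors, so a subject's Visits 3, 4 and 5 count as if they came from three different people. Averaging over visits then appears to reduce the error variance by the full factor of three. With positively correlated visits the true reduction is smaller. The reported SE of the all-visits treatment effect is too small, its CI too narrow and its p-value too low.

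This touches the confirmatory core of the SAP. The hypotheses in Section 2.5 name no visit and no primary visit is designated, so the all-visits contrast is a natural reading of the main test. The same model serves both key efficacy variables. Benjamini-Hochberg cannot repair the result, because it assumes that the p-values it receives are valid.

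**Working it through.** **Inputs from the documents.** 33 subjects, 22 active and 11 placebo (SAP Section 5). Two-sided 5% (Section 8.4). Three post-baseline visits up to Visit 5: for SANDE, the modified "Dry Eye Questionnaire will be collected at Visit 1 and Visits 3" to 7; for GLIA, Visits 3, 4 and 5.

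**Input not in the documents.** The within-subject correlation ρ left after baseline adjustment. Assumed values are 0.3, 0.5 and 0.7, with equal correlation between visits, equal variances and complete data.

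**Rows and df.** 33 × 3 = 99 rows. The fixed effects take 2 × 3 treatment-by-visit means plus 1 baseline slope = 7 parameters, leaving 99 − 7 = 92 residual df. These are maxima: Section 16 records one early discontinuation and removes LOCF, and Section 13.2 (SANDE) says "Subjects whose values are all 0 for a given symptom for all visits will not be included in the analysis for that symptom". Losing one whole subject leaves the type I error figures below unchanged.

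**Large-sample formula.** With m visits:
- True variance of the visit-averaged difference: σ²(1/22 + 1/11)[1 + (m−1)ρ]/m
- Variance the model uses: σ²(1/22 + 1/11)/m
- True SE ÷ reported SE = √[1 + (m−1)ρ]
- Actual α = 2{1 − Φ(1.96 ÷ SE ratio)}

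For m = 3, the SE ratio is √1.6 = 1.265, √2 = 1.414 and √2.4 = 1.549. Actual α is 12.1%, 16.6% and 20.6%. At ρ = 0 the formula returns the plan's own 5.0%.

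**Finite-sample version.** The pooled residual variance mixes 30 between-subject df and 62 within-subject df. Its expectation in units of σ² is {30[1 + 2ρ] + 62(1 − ρ)}/92. At ρ = 0.5 that is (60 + 31)/92 = 0.989, so the SE ratio is √(2/0.989) = 1.42. Averaging the t-test over the chi-square distributions gives:

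| Assumed ρ | True SE ÷ reported SE | Actual type I error, all visits |
|---|---|---|
| 0.3 | 1.27 | 12.2% |
| 0.5 | 1.42 | 16.8% |
| 0.7 | 1.56 | 21.0% |

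**Simulation of the model as written** (10,000 null trials per setting): 11.9%, 17.4% and 20.9%, and 4.9% at ρ = 0. The simulation error is about 0.3 to 0.4 percentage points for the three inflated rates.

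**Milder correlation assumptions, three visits.**
- ρ = 0.1 or 0.2: 7.4% or 9.8%.
- Correlation decaying with visit order, adjacent visits 0.3/0.5/0.7: about 10.5%/15.1%/19.4%.
- If 0.3/0.5/0.7 is the raw correlation including baseline, the adjusted value is r/(1 + r) = 0.23/0.33/0.41. Type I error is 10.5%/13.0%/14.8% and the SE ratio 1.21/1.30/1.36.

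**Other tests from the same model.** Single-visit contrasts: 4.9 to 5.9% under equal variances. With visit variances of 0.6, 1 and 1.6 and ρ = 0.5, the last-visit contrast is about 11%. The treatment-by-visit test errs the other way: 1.6%, 0.4% and 0.02%.

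**If the Visit 2 post-dose GLIA record enters.** The SAP does not say. It would give 33 × 4 = 132 rows and 132 − 9 = 123 df. If that record behaved like the other visits, type I error would be 15.6%/21.8%/27.0%. A rating 30 to 60 minutes after the first dose may well not behave so; this is a side case.

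**Secondary analyses.** The additional model in Section 13.1.1 also stacks both eyes without a subject term. At an assumed between-eye correlation of 0.5 to 0.8 and three visits, the all-visits test runs at 21 to 36% and the single-visit test at 11 to 16%. Section 13.5.3 carries the clinic model to the continuous slit-lamp scores.

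**The case against.** *The code is only pseudo-code.* It is labelled so, and other blocks are loose: eye type is missing from CLASS in the two-eye model, and the diary block's RANDOM statement names no subject. The executed program may differ. But the prose of Section 13.1.1 gives no covariance either, while the diary section gives one in both prose and code. A programmer following the SAP would leave it out of the clinic model.

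*The all-visits test is not declared decisive.* This is true, and Section 8.5 does not say which p-values enter the Benjamini-Hochberg family. By-visit contrasts are nearly correct under equal variances, and the by-visit t-tests by eye type are unaffected. The protocol's biostatistics section treats inference as additional description of the data. Against this, SAP Section 1 says its methods supersede the protocol's, and the SAP sets hypotheses, a 5% level and multiplicity control. Its all-visits CIs would also be wrong as description.

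*The size rests on an assumed correlation.* This stands. The direction follows from any positive ρ; 21.0% belongs to the top of the assumed range and is not an expected value.

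**Conclusion.** The point holds: the primary model is wrong as written for the all-visits treatment effect on GLIA and SANDE, and it must be fixed. With three visits and assumed ρ of 0.3 to 0.7, type I error is 12.2% to 21.0% against a nominal 5%, and the true SE is 1.27 to 1.56 times the one reported. The milder raw-correlation reading still gives 10.5% to 14.8%. These figures assume complete data and equal variances and correlations across visits; at ρ = 0 there is no error. Single-visit contrasts in the primary model are close to nominal only while variances are similar across visits. The two-eye and slit-lamp analyses share the fault but are secondary and unadjusted for multiplicity.

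**What to change.** **Primary model (GLIA, SANDE and the continuous slit-lamp scores).** Add the subject to CLASS, add `repeated VISIT / subject=SUBJ type=UN;` and use `ddfm=KR`. Prespecify a fallback such as `type=CS` in case UN does not converge. In null simulations with three visits (1,500 runs per setting), UN with Kenward-Roger df gave all-visits type I error of 5.2%, 5.1% and 4.5% at ρ = 0.3, 0.5 and 0.7, with no failed fits. ANCOVA on each subject's mean change is another valid repair for the all-visits test (4.9 to 5.3% with three visits).

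State whether the Visit 2 post-dose record enters the GLIA model.

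**Two-eye model.** Put eye type and subject in CLASS and allow a higher correlation between eyes at the same visit than across visits, for example `repeated EYETYPE VISIT / subject=SUBJ type=UN@UN;` with Satterthwaite df. As a prespecified fallback, use `random intercept VISIT EYETYPE / subject=SUBJ;` with `ddfm=KR`.

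**Cost.** A few lines of SAS in two model specifications and some convergence checking, with no new data. All-visits CIs in the primary model become roughly 1.2 to 1.6 times as wide under the assumed correlations; that is the uncertainty the present model leaves out.
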